3.7.2 Investigational Medicinal Product Preparation

The investigator, or an approved representative (for example, pharmacist), will ensure that all IMP is reconstituted and dispensed by qualified staff members.

3.7.3 Investigational Medicinal Product Accountability

All IMP and any other study-related material is to be accounted for on the IMP accountability log provided by the sponsor. It is essential that all used and unused supplies are retained for verification (by the sponsor or sponsor's representative). The investigator should ensure adequate records are maintained in the IMP accountability log. The destruction of used and unused IMP should be carried out only after any discrepancies have been investigated and satisfactorily explained, and the reconciliation has been accepted. The IMP will be destroyed either on site or in the ISF.

3.8 Maintenance of Randomisation and Blinding

The investigator will under no circumstances change the randomisation number and the treatment arm allocated to the subject via the IWRS. As this is an open-label study, there is no blinding of investigator or subjects.

To mitigate any potential bias due to the open-label design of this study, E₂, LH and FSH concentrations will be evaluated centrally.

3.9 Source Data Recorded on the Case Report Form

Data will be collected in the eCRF in compliance with Food and Drug Administration (FDA) 21 Code of Federal Regulations (CFR) Part 11. As required by GCP, the sponsor-assigned monitor will verify, by direct reference to the source documents, that the data required by the protocol are accurately reported on the eCRF.

The source documents must, as a minimum, contain a statement that the subject is included in a clinical study, the date that informed consent was obtained prior to participation in the study, the identity of the study, diagnosis and eligibility criteria, visit dates (with subject status), IMP administration details, and any AEs and associated concomitant medication.

As required by ICH GCP Section 6.4.9, if some items are recorded directly on the eCRF and are considered as source data, the identification of these data must be documented and agreed between the investigator and the sponsor.

Definition for source data and source documents are given below:

- **Source data:** All original records and certified copies of original records of clinical findings, observations, or other activities necessary for the reconstruction and evaluation of the study. Source data are contained in source documents (original records or certified copies).
- **Source documents:** Original documents, data and records (for example, hospital records, clinical and office charts, laboratory notes, memoranda, subjects' diaries or evaluation checklists, pharmacy dispensing records, recorded data from automated instruments, copies or transcriptions certified after verification as being accurate copies, microfiches, photographic negatives, microfilm or magnetic media, x rays, subject files, and records kept at the pharmacy, at the laboratories and at medicotechnical departments involved in the clinical study).

The subject must have consented to their medical records being viewed by the sponsor's authorised personnel, and by local, and possibly foreign, competent authorities (CAs). This information is included in the informed consent.

4 SELECTION AND WITHDRAWAL OF SUBJECTS

4.1 Inclusion Criteria

All subjects must fulfil all of the following criteria to be included in the study:

- (1) Female subjects aged from 18 to 45 years inclusive at the date of informed consent.
- (2) Provided written informed consent.
- (3) A history of active and regular menstrual cycles of 21 to 35 days (inclusive) in the 6 months prior to the screening visit.
- (4) A diagnosis of endometriosis, confirmed by laparoscopy or laparotomy within 10 years prior to the screening visit.
- (5) Requires treatment with a GnRH agonist for a period of 6 months in the judgement of the investigator.
- (6) A negative pregnancy test prior to the start of treatment.
- (7) Not at risk of pregnancy, i.e. subjects of childbearing potential must be actively using barrier contraception throughout the study treatment until menses resume.

4.2 Exclusion Criteria

Subjects will not be included in the study if any of the following criteria are met:

- (1) Subject is menopausal.
- (2) Subject is pregnant or lactating.
- (3) A current history of undiagnosed abnormal genital bleeding.
- (4) Received treatment with a GnRH agonist within 6 months prior to the screening visit.
- (5) A history of hypersensitivity to GnRH agonists and/or any of the excipients.
- (6) Received any other hormonal treatment within 3 months prior to the screening visit (oestrogens, progestogens, danazol, gestrinone and cyproterone acetate etc).
- (7) Has been treated for endometriosis with traditional Chinese medicine within 1 month prior to screening.
- (8) It is anticipated that the subject will require surgery during the study period.
- (9) Chronic pelvic pain that is not caused by endometriosis, that would interfere with the assessment of endometriosis-associated pelvic pain.
- (10) A significant endocrine disorder (except controlled diabetes mellitus).
- (11) Known history of human immunodeficiency virus (HIV) infection.
- (12) Known history of chronic active hepatitis, including viral hepatitis carriers (hepatitis B or hepatitis C).
- (13) Clinically significant hepatic (any liver enzyme $> 2\times$ the upper limit of normal (ULN)) or renal (creatinine $> ULN$) abnormalities or any other dysfunction according to the investigator's judgement.
- (14) Any psychiatric illness, severe or unstable known illness that in the investigator's opinion could affect the safety, conduct or outcome of the study.
- (15) Use of concomitant therapy, which in the investigator's opinion may interfere with the evaluation of study treatment efficacy and safety.

- (16) Treatment with any other experimental drug or device within 90 days prior to the screening visit and/or expectation of treatment with any other experimental drug or device during the conduct of the study.
- (17) Any malignancy except curatively-treated basal cell skin cancer.
- (18) Unable or unwilling to comply with the protocol.
- (19) A history of alcohol and/or drug abuse.
- (20) Abnormal pelvic type B ultrasonography finding that would contraindicate the use of triptorelin.

4.3 Subject Withdrawal Criteria and Procedures

In accordance with the Declaration of Helsinki, each subject is free to withdraw from the study at any time. The investigator also has the right to withdraw a subject from the study in the event of concurrent illness, AEs, pregnancy (see Section 8.1.5), or other reasons concerning the health or wellbeing of the subject, or in the case of lack of cooperation. In addition, a subject may be withdrawn from the study as described in Sections 3.6, 6.2 and 8.1.7.

Should a subject decide to withdraw from the study after administration of the IMP, or should the investigator decide to withdraw the subject, all efforts will be made to complete and report the observations up to the time of withdrawal as thoroughly as possible. A complete final evaluation at the time of the subject's withdrawal should be made (see Section 5.2.4.4) and an explanation given of why the subject is withdrawing or being withdrawn from the study.

The reason for and date of withdrawal from the study must be recorded on the eCRF. If a subject withdraws consent, every attempt will be made to determine the reason. If the reason for withdrawal is an AE or a clinically significant laboratory test abnormality, monitoring will continue until the event has resolved or stabilised, until the subject is referred to the care of a local health care professional, or until a determination of a cause unrelated to the IMP or study procedure is made. The specific AE or test result(s) must be recorded on the eCRF. All evaluations should be performed, according to the protocol, on the last day the subject receives IMP, or as soon as possible thereafter.

5 STUDY PROCEDURES

5.1 Study Schedule

The schedule of procedures and assessments during the study is summarised in [Table 2](#). Procedures and assessments specific to the PK and PD subgroups are summarised in [Table 3](#) and [Table 4](#).

Table 2 Study Procedures and Assessments (All Subjects)

	Screening period	Treatment period										Follow up period [a]		
	Visit 1	Visit 2	Visit 3	Visit 4	Visit 5	Visit 6	Visit 7	Visit 8	Visit 9	Visit 10	Visit 11	End of study/early withdrawal visit		
Procedures and assessments	Screening up to -5 weeks	Baseline	Week 4	Week 8	Week 12	Week 16	Week 20	Week 24	Week 28	Week 32	Week 36	Within 15 days after menses recovery or Week 40[b]		
Visit window (days)	-35 to -1	Day 1	Day 29 ±3	Day 57 ±3	Day 85 ±3	Day 113 ±3	Day 141 ±3	Day 169 ±3	Day 197 ±3	Day 225 ±3	Day 253 ±3	(Day 281±3 days)		
Prior and concomitant medication/therapies	X	X	X	X	X[j]	X[j]	X[j]	X	X	X	X	X		
Status of menses	X	X	X	X	X	X	X	X	X	X	X	X		

AE=adverse event; E₂=oestradiol; ECG=electrocardiogram; FSH=follicle stimulation hormone; LH=luteinising hormone; PK=pharmacokinetic; VAS=visual analogue scale

- a during the follow up period, the first visit after menses recovery, or Week 40 (whichever is earlier) will be considered the final visit (end of study). The end of study visit should be a clinic visit. Follow up visits prior to the end of study visit will be telephone contact visits
- b or upon early withdrawal from the study
- c samples taken pre-dose, where applicable
- d only if subject's menses do not recover before Week 40
- e subject height and weight will be assessed at screening only
- f samples for clinical laboratory testing will be taken after at least 8 hours fasting
- g a result within 1 month prior to the screening visit will be acceptable
- h optional, based on the subject's disease condition, as judged by the investigator
- i study treatment must be initiated during the subject's follicular phase (first to fifth day of menses period)
- j from Week 12, after the primary endpoint evaluation, "add back" treatment will be permitted if needed according to the investigator's judgement. "Add back" treatment will be recommended as, but not limited to, tibolone 2.5 mg once daily

Table 3 Full PK/PD Assessments Day 1 to Week 12 (PK/PD Subgroup Subjects)

Assessment[a]	Treatment period											
	Day 1	Week 1 (hours post Day 1 dosing)		Week 2	Week 3	Week 4	Week 6	Week 8	Week 10	Week 12		
Assessment time (study day/hours postdose)[b]	Day 1	24	48	168	Day 15	Day 22	Day 29	Day 43	Day 57	Day 71	Day 85	
PK (3M)	X[c]	X	X	X	X	X	X	X	X		X[c]	
PK (1M)	X[c]	X	X	X	X	X	X[d]		X[d]	X	X[d]	
PD (E ₂ , FSH and LH)				X	X	X						
AEs	X		X		X	X	X	X	X	X	X	
Prior and concomitant medication/therapies	X		X		X	X	X	X	X	X	X	

1M=triptorelin acetate PR 1-month; 3M=triptorelin pamoate PR 3-month; AE=adverse event; E₂=oestradiol; FSH=follicle stimulating hormone; LH=luteinising hormone; PD=pharmacodynamics; PK=pharmacokinetics.

- a assessments to be conducted with samples from the subjects in the full PK/PD subgroup (comprising up to 16 subjects receiving 3M and up to 16 subjects receiving 1M, to be enrolled at selected sites)
- b time windows for full PK/PD assessments will be defined in the Study Manual
- c samples taken predose and 0.5, 1, 2, 4, 8 and 12 hours postdose
- d samples taken predose

Table 4 Full PK/PD Assessments Week 13 to End of Study (PK/PD Subgroup Subjects)

Assessment[a]	Treatment period													Follow up period			
	Week 13 (hours post Week 12 dosing)		Week 14	Week 15	Week 16	Week 18	Week 20	Week 24	Week 28	Week 32	Week 36	End of study/ early withdrawal					
Assessment time (study day/hours postdose)[b]	24	48	168	Day 99	Day 106	Day 113	Day 127	Day 141	Day 169	Day 197	Day 225	Day 253	See Table 2				
PK (3M)	X	X	X	X	X	X	X	X	X	X	X	X	X				
PK (1M)																	
PD (E ₂ , FSH and LH)																	
AEs		X		X	X	X	X	X	X	X	X	X	X	X			
Prior and concomitant medication/therapies		X		X	X	X	X	X	X	X	X	X	X	X			

IM=triptorelin acetate PR 1-month; 3M=triptorelin pamoate PR 3-month; AE=adverse event; E₂=oestradiol; FSH=follicle stimulating hormone; LH=luteinising hormone; PD=pharmacodynamics; PK=pharmacokinetics.

a assessments to be conducted with samples from the subjects in the full PK/PD subgroup (comprising up to 16 subjects receiving 3M and up to 16 subjects receiving 1M; to be enrolled at selected sites) only

b time windows for full PK/PD assessments will be defined in the Study Manual

The total volume of blood drawn for all evaluations throughout this study for each subject not in the full PK/PD subgroup will be approximately 47.5 mL (Table 5).

Additional blood samples for subjects in the full PK/PD subgroup are presented in Table 6. The total volume of blood drawn (including blood samples taken from all subjects, and additional PK/PD samples) will be 121.5 mL for subjects receiving triptorelin pamoate 3-month and 93.5 mL for subjects receiving triptorelin acetate 1-month.

Table 5 Blood Volume Calculation (All Subjects)

Description	Number of samples	Volume (mL)	Total volume (mL)
Haematology	3	2	6
Blood biochemistry	3	2.5	7.5
E ₂ , FSH and LH	6	4	24
Sparse PK	5	2	10
Total volume (mL)			47.5

E₂=oestradiol; FSH=follicle stimulating hormone; LH=luteinising hormone; PK=pharmacokinetics.

Table 6 Additional Blood Samples (Full PK/PD Subgroup)

Description	Number of samples	Volume (mL)	Total volume (mL)
Subjects receiving triptorelin pamoate 3-month			
E ₂ , FSH and LH	4	4	16
PK	29	2	58
Total volume (mL)			74
Subjects receiving triptorelin acetate 1-month			
E ₂ , FSH and LH	4	4	16
PK	15	2	30
Total volume (mL)			46

E₂=oestradiol; FSH=follicle stimulating hormone; LH=luteinising hormone; PD=pharmacodynamics; PK=pharmacokinetics.

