5.2 Study Visits

5.2.1 Procedures for Screening and Enrolment (Visit 1; up to -5 weeks)

A signed and dated informed consent form will be obtained before screening procedures. Evaluations obtained as part of routine medical care and performed during the screening period may be used in place of the study specific evaluations. Subjects will acknowledge and agree to the possible use of this information for the study by giving informed consent.

After informed consent is obtained, subjects who are screened will be allocated a subject number. All screened subjects must be identifiable throughout the study. The investigator will maintain a list of subject numbers and names to enable records to be found at a later date if required.

Rescreening will not be permitted in this study.

The screening visit (Visit 1) will take place up to 5 weeks prior to the first dose of IMP being administered. The following assessments will be performed at screening:

- Demographic data (date of birth, sex, ethnicity, and race)
- Significant medical or surgical history, including ongoing medical conditions, AEs, gynaecological history, date of last menses
- Eligibility check (inclusion/exclusion criteria)
- Physical examination (including subject height and body weight)
- Pelvic examination
- Vital signs (sitting blood pressure and heart rate)
- Laboratory safety tests (blood sampling for biochemistry, haematology and urinalysis)

- Urine pregnancy test, method of contraception
- 12-lead ECG
- Pelvic type-B ultrasound scan (a result obtained within 1 month of the screening visit will be acceptable)
- Prior and concomitant medications/therapies (including medications and therapies for endometriosis)
- Record date of onset of last menses and expected date of onset of next menses

Each investigator will also maintain a record of all subjects screened into the study (i.e. who signed the informed consent form). Records up to the time of premature subject termination should be completed and the primary reason for termination will be recorded.

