The severity of endometriosis-associated pain will be assessed by the subject at Day 1 (baseline), Weeks 4, 8, 12, 16, 20, 24, and at the end of study visit using a 10 cm VAS. Subjects will be asked to assess their most severe endometriosis-associated pain over the preceding 4 weeks. For the Day 1 (baseline) assessment, if subjects had undergone endometriotic surgery within the previous 4 weeks, they will be asked to assess their most severe endometriosis-associated pain postsurgery. The VAS to be used is presented in Appendix 1.

7.3.3 *Recovery of Menses*

Status of menses recovery will be assessed at all study visits, including the follow-up period (Weeks 28, 32, 36 and at the end of study visit). The date of menses (if available) will be recorded at the end of study visit. Time to menses recovery will be defined as the time (in days) between the date of the last dose of study drug and the date of the first day that the subject observed menstrual bleeding of the next menses period. Any subjects withdrawing from the study without menstrual bleeding will be censored in this analysis at the date of withdrawal. Any subjects without menstrual bleeding prior to the end of study visit will be censored in this analysis at the date of the end of study visit.

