8.4 Pelvic Type B Ultrasound Scan

A pelvic type B ultrasound investigation will be performed at screening (Visit 1; a result within 1 month prior to screening will be acceptable) and at Week 24 (Visit 8). An additional (optional) scan may be conducted at Week 12 (Visit 5) based on the subject's condition, as judged by the investigator.

Any clinically significant pelvic type B ultrasound findings (abnormalities) observed during the study will be reported as AEs.

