6 DATA HANDLING

6.1 Time points and Visit Windows

Day 1 is defined as the day of first dose of IMP treatment. Relative days after Day 1 are calculated as (assessment date – Day 1 date) + 1. Relative days prior to Day 1 are calculated as (assessment date – Day 1 date). The day prior to Day 1 is Day -1.

Unless specified otherwise, baseline is defined as the last available assessment prior to the first dose of IMP; if assessment time and/or drug taken time is not collected, the assessment performed on the same day as first dose of IMP will be considered as baseline; if assessment date is missing, the assessments at the scheduled visits of screening (Visit 1) and Day 1 or baseline (Visit 2) will be considered as pre-baseline visits in flag baseline.

By-visit analyses on data will be analysed according to the scheduled visits outlined in the protocol and/or eCRF (Week xx). No visit windows will be applied for summary and analysis.

If subject early discontinued study, the measured safety and efficacy variables at early discontinued visit are collected in “End of study/early withdrawal visit”. Then the early withdrawal visit of safety and efficacy endpoints (except PD sampling) will be re-mapped to the visits using the time windows in Table 1.

Table 1 Scheduled Visits and Time Window

Scheduled Visit at Study Site	Target Day of the Visit	Protocol Visit Window	Time Window to Re-map End of Study Visit or Early Withdrawal Visit
Baseline	Day 1	Day 1	Day 1
Week 4	Day 29	Target Day \pm 3 days	Day 26 – Day 53
Week 8	Day 57	Target Day \pm 3 days	Day 54 – Day 81
Week 12	Day 85	Target Day \pm 3 days	Day 82 – Day 109
Week 16	Day 113	Target Day \pm 3 days	Day 110 – Day 137
Week 20	Day 141	Target Day \pm 3 days	Day 138 – Day 165
Week 24	Day 169	Target Day \pm 3 days	Day 166 – Day 193
Week 28	Day 197	Target Day \pm 3 days	Day 194 – Day 221
Week 32	Day 225	Target Day \pm 3 days	Day 222 – Day 249
Week 36	Day 253	Target Day \pm 3 days	Day 250 – Day 277
End of study visit (Week 40)	Day 281 or within 15 days after menses recovery	Target Day \pm 3 days	\geq Day 278

Data from end of study visit or early termination assessments will be combined with data from scheduled visits in the by-visit analyses only if no scheduled visit data for the same parameters at that visit.

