7.7.6 Pelvic type B ultrasound

The pelvic type B ultrasound scan will be performed at screening (Visit 1), Week 12 (Visit 5, optional based on investigator judgment) and Week 24 (Visit 8).

Shift tables of test results (normal, abnormal not clinically significant, abnormal clinically significant) from baseline to each scheduled post-baseline visit and final visit will be presented by each treatment group and overall.

All pelvic type B ultrasound scan data collected during the study will be presented in subject listings.

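### A pelvic ultrasound taken before recent endometriosis surgery can serve as the baseline, so the ultrasound shift tables can mix the effect of surgery with change on treatment (low severity)

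*Protocol*

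**What the plan says.** **Ultrasound timing.** Protocol Table 2 footnote g accepts an earlier scan: "a result within 1 month prior to the screening visit will be acceptable". Section 5.2.1 repeats this in the screening list and Section 8.4 in the safety methods ("a result within 1 month prior to screening will be acceptable"). After screening, a scan is required only at Week 24; the Week 12 scan is optional (8.4). The pre-dose list for Visit 2 (5.2.2) contains no ultrasound.

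**Recent surgery.** Inclusion 4 asks for a diagnosis by laparoscopy or laparotomy in the 10 years before screening and sets no minimum interval. Section 7.3.2 has a Day 1 rule for pain that applies "if subjects had undergone endometriotic surgery within the previous 4 weeks": the woman rates only her pain since the operation. Appendix 1 carries the same instruction.

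**Use of the scan.** Exclusion 20 is "Abnormal pelvic type B ultrasonography finding that would contraindicate the use of triptorelin". Under SAP 6.1, "baseline is defined as the last available assessment prior to the first dose of IMP". SAP 7.7.6 then plans "Shift tables of test results (normal, abnormal not clinically significant, abnormal clinically significant) from baseline to each scheduled post-baseline visit" and the final visit, by arm and overall.

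**The concern.** The plan recognises that an operation shortly before Day 1 makes an earlier pain rating unsuitable as a baseline, and it restricts that rating to the time after surgery. It has no matching rule for ultrasound, although surgery can directly change what a scan shows.

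A lesion removed at operation but visible on the reused scan could appear in the shift table as a move from abnormal to normal during treatment. A post-operative finding absent from that scan could appear as new and, if clinically significant, would be reported as an adverse event under Protocol 8.4. Eligibility under exclusion 20 would be judged on an image of the pelvis before the operation. Ultrasound is a named safety evaluation (Protocol 3.2.5, SAP 3.4), so its table should describe change since treatment began.

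**Working it through.** The plan states no figure on this point. The check is whether its rules, read together, allow the problem sequence.

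**Inputs**
- Look-back for the scan: up to 1 month before screening, taken as 28 to 31 days (footnote g, 5.2.1, 8.4).
- Screening: "The screening visit (Visit 1) will take place up to 5 weeks prior to the first dose of IMP being administered", that is Day -35 to Day -1 (5.2.1, Table 2).
- Surgery foreseen within 4 weeks (28 days) before Day 1 (7.3.2, Appendix 1).
- Day numbering: Day -n is n days before Day 1 (SAP 6.1).

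**Step 1. Oldest permitted scan at first dose.** 28 + 35 = 63 days; 31 + 35 = 66 days. The scan can be about 63 to 66 days old. This is the age of the image, not the interval in which surgery is likely (see the objection).

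**Step 2. Does the sequence fit?** Take a scan on Day -40, surgery on Day -25, screening on Day -15, then the first dose on Day 1.
- Scan to screening: 40 - 15 = 25 days, inside the 1-month look-back.
- Screening to first dose: 15 days, inside 35.
- Surgery to first dose: 25 days, inside the 28 days that the pain rule foresees.
- Surgery precedes screening by 25 - 15 = 10 days, so the restrictions on surgery during the study do not apply.

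Every step is permitted, and no section requires a new scan.

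**Step 3. Which scan becomes baseline?** If the screening scan is replaced by the Day -40 result and none is added before dosing, the last available pre-dose assessment is the Day -40 scan, taken 15 days before the operation.

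**Step 4. What enters the shift table?** The next required scan is at Week 24 (Day 169), which is 168 + 40 = 208 days after the baseline image. If the optional Week 12 scan and any unscheduled scan are absent, her whole entry rests on one pre-operative and one Week 24 image. SAP 7.7.6 has no flag or split for surgery in between.

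**Step 5. Pain and ultrasound compared.** For the same woman, the VAS baseline describes the time after surgery and the ultrasound baseline the time before it.

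**Step 6. How many women?** The count would be 300 × (share reusing an earlier scan) × (share of those operated on after it) × (share of those not rescanned before dosing). The documents give none of the three shares, so the count cannot be computed.

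**The case against.** **It needs three conditions together.** An earlier scan must be reused, surgery must have followed it, and no later pre-dose scan may exist. Footnote g permits reuse but does not require it, and under SAP 6.1 any post-operative scan made before dosing replaces the older one. This stands. A reader might infer that the tables as a whole report surgery as a drug effect. The documents do not support that: the mixing is possible for some women, and SAP 7.7.6 tabulates shifts without attributing them to a cause.

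**The surgical window is shorter than the age of the scan.** Protocol 3.5 counts screening as part of the study, exclusion 8 bars women expected to need surgery in the study period, and 6.2 does not permit surgery during the study. Surgery between screening and Day 1 is therefore largely closed off. The exposure is mainly the month before screening, and reading the 63 to 66 days as the surgical window would overstate it.

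**Recent surgery is foreseen, not shown to be common.** Diagnoses may be up to 10 years old, and Protocol 1.1 describes GnRH analogues as given before or after surgery. Any assumed percentage of women affected would have no basis in the documents.

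**Other safeguards exist.** Surgical history and a pelvic examination are taken at screening (5.2.1), and pretreatment events and eligibility are reviewed on Day 1 (5.2.2). The investigator assesses causality for every adverse event (8.1.3). A condition known before dosing is not treatment-emergent unless it worsens (10.4.8, SAP 7.7.1). These reduce the risk to adverse-event and eligibility judgements, though an unrecognised post-operative finding could still pass. They do not correct the shift table.

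**Conclusion.** The concern holds at low severity. For women whose reused scan preceded surgery and was not repeated before dosing, the stated rules give a wrong ultrasound baseline. This is more than missing detail, because SAP 6.1 determines that the pre-operative image is used.

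The effect is limited to the within-arm and overall ultrasound shifts, some adverse-event judgements, and exclusion 20. A reader might infer a bias between arms, but the documents do not support a material one. Scan and surgery both precede randomisation at Visit 2, so the problem should fall on both arms about equally on average. The surgical-history stratum helps only in part, since it separates previous from no previous surgery and not recent from distant. The primary E₂ endpoint, its margin and the sample size do not use the scan.

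The conclusion assumes that some sites reuse scans as the protocol allows and that some of those women were operated on in between. The documents permit both and quantify neither.

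**What to change.** **Protocol (Table 2 footnote g, 5.2.1, 8.4).** Accept an earlier scan only if no endometriotic or pelvic surgery took place between that scan and the screening visit. Otherwise use the screening scan already scheduled.

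**SAP 7.7.6.** Keep the main shift table on the full Safety Set, because Protocol 10.4.8 and SAP 7.7 base safety summaries on it; removing women from that table would conflict with both. Flag women whose baseline scan predates surgery, using the scan date and the surgery date already used in SAP 7.4, and add a supplementary shift table without them.

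**Partial surgery dates.** SAP 6.2.2 sets these to the first day of the known month or year. That can place an operation before a scan it actually followed, and the woman would be missed. For the flag, treat such dates as undetermined where the known part does not settle the order.

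**Cost.** One condition in the protocol, a flag and one extra table in the SAP. Some women have the scheduled screening scan instead of reusing an old one. The flag would also show how many women are affected.
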